
Trial Assessments:
	
Screening: Informed consent, medical history (including ADPKD updates, as required), determination of eligibility through inclusion/exclusion criteria, dietary review, vital signs, clinical laboratory assessments, physical examination, urine pregnancy test (women of child-bearing potential only [WOCBP]), concomitant medications and laboratory tests to determine eligibility.
 
Safety: Adverse events (AEs), vital signs, directed physical examination, dietary review, self-assessed drug tolerability, serum chemistry tests (including serum transaminases, alkaline phosphatase, bilirubin, and serum sodium) and concomitant medications.
 
CCI [REDACTED]
 
CCI [REDACTED]

Criteria for Evaluation
	
Safety:
 
 • AEs • Vital signs • Clinical laboratory assessments • Serum transaminase elevations for frequency (2x, 3x, 5x and 10x ULN), time to onset, time to peak levels, time of offset (< 3x, 2x, or 1x ULN), response to de-challenge and re-challenge and frequency of progression to Hy’s laboratory criteria (ALT or AST > 3x ULN and BT > 2x ULN without alkaline phosphatase ≥ 2x ULN) • Serum sodium excursions above 145, 150, or

Protocol 156-13-211

	
155 mmol/L or below 135, 130, or 125 mmol/L
 
CCI [REDACTED]
 
[REDACTED]
 
[REDACTED]

Statistical Methods:
	
Sample size: Sample size was not determined by a formal computation to achieve a target power. No efficacy analyses are planned. It is expected that approximately 2,500 subjects may enroll from previous tolvaptan trials.
 
Analysis datasets:
 
 • Enrolled Population: all subjects who were enrolled to this open-label trial • Safety Population: all subjects in the Enrolled Population who take at least 1 dose of IMP 
Safety analyses: Safety analysis will be conducted based on standard safety variables, including AEs, clinical laboratory data, physical examinations and vital signs. Potentially clinically significant results in laboratory tests identified using prospectively defined criteria, including criteria on liver enzyme elevations, will be summarized.

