^eCentral laboratory non-fasting serum laboratory tests will be performed. All subjects must be monitored for hepatic safety monthly until they have known tolvaptan exposure data of at least 18 months. After that, and following the approval of the medical monitor, hepatic monitoring will take place every 3 months. Trial 156-13-210 subjects who are eligible for this trial will have trial visits/hepatic monitoring monthly for the first 18 months of this trial then every 3 months thereafter, because their tolvaptan exposure will be unknown. Once unblinding occurs, it can be determined which subjects received tolvaptan in Trial 156-13-210. These subjects may have their trial visits/hepatic transaminase monitoring changed to every 3 months sooner as their previous tolvaptan exposure in Trial 156-13-210 can count towards the 18 month threshold. Subjects who enroll from other ADPKD tolvaptan trials will be monitored for hepatic safely monthly for their first 18 months they are in this trial.

^fHepatitis testing at screening will be optional. If hepatitis testing is performed, then both pre- and post-counseling activities relating to hepatitis testing are to be carried out based on local requirements and best practices. Upon request, if clinically indicated and approved by the medical monitor, subjects may have the following evaluations in addition to the protocol-specified chemistry panel: serum calcium, phosphorous, parathyroid hormone, vitamin D, and bicarbonate levels.

^gA full liver function panel (AST, ALT, alkaline phosphatase, BT) will be done at screening. All other liver function tests at subsequent visits are for ALT only, unless otherwise clinically indicated. An ALT elevation > 2 × ULN should trigger prompt testing of hepatic function within 72 hours. Any transaminase or bilirubin values which exceed 2 × ULN should prompt immediate retesting within 72 hours. While values remain in an abnormal range, testing frequency should be increased to at least weekly for the first month, gradually returning to monthly, and every 3 months as indicated by the results. Local liver function panel analyses will also be performed more frequently, if necessary.

^hUrine osmolality is optional.

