2. CCI [REDACTED]
3. Record vital signs (post-void weight, seated heart rate, and calibrated blood pressure measurement).
4. Collect blood for central laboratory assessments for serum sodium, serum creatinine, and ALT (see [Section 3.7.2.4](#)).

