2. CCI [REDACTED]
3. Record vital signs (post-void weight, seated heart rate, and calibrated blood pressure measurement).
4. Collect blood for central laboratory assessments serum sodium, serum creatinine, ALT (see [Section 3.7.2.4](#)).

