7.5.2.3 Clinical Laboratory Assessments

Summary statistics for changes from baseline in clinical laboratory measurements will be provided for the Safety Population. Potentially clinically significant results in laboratory

Protocol 156-13-211

CCI [REDACTED]

8 Management of Investigational Medicinal Product

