Synopsis, Trial Duration and Section 3.1, Type/Design of Trial	Trial duration is planned to continue 
 • Until the last subject from Trial 156-13-210 completes 18 months of tolvaptan treatment in this trial • Subjects enrolling from other trials will conclude their participation once tolvaptan becomes available through routine prescription or through a CCI [REDACTED] Trial 156-13-210 subjects may opt to conclude their participation in this trial if tolvaptan becomes available before they complete 18 months of treatment in this trial 	Trial duration is planned to continue 
 • Until the last subject from Trial 156-13-210 completes 18 months of tolvaptan treatment in this trial • All subjects will receive at least 18 months of tolvaptan treatment in the extension study. Trial 156-13-210 subjects or subjects enrolling from other trials may opt to conclude their participation in this trial if tolvaptan becomes available before they complete 18 months of treatment in this trial
Section 3.7, Trial Procedures, Table 3.7-1, Schedule of Assessments	Footnote g §A full liver function panel (AST, ALT, alkaline phosphatase, BT) will be done at screening. All other liver function tests at subsequent visits are for ALT only, unless otherwise clinically indicated. Any transaminase or bilirubin values which exceed 2 × ULN should prompt immediate retesting within	Footnote g §A full liver function panel (AST, ALT, alkaline phosphatase, BT) will be done at screening. All other liver function tests at subsequent visits are for ALT only, unless otherwise clinically indicated. Any transaminase values which exceed 2 × ULN should prompt immediate retesting within 72 hours. While

Protocol 156-13-211

Location	Old Text	Updated Text
	72 hours. While values remain in an abnormal range, testing frequency should be increased to at least weekly for the first month, gradually returning to monthly, and every 3 months as indicated by the results. Local liver function panel analyses will also be performed more frequently, if necessary.	values remain in an abnormal range, testing frequency should be increased to at least weekly for the first month, gradually returning to monthly, and every 3 months as indicated by the results. Local liver function panel analyses will also be performed more frequently, if necessary.

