8.1.2 Handling of Missing/Incomplete AE start/stop dates

Incomplete/missing start dates of AEs will be estimated by the following rules:

- If the year is missing, default to the same year the patient received the first dose of study medication, or the stop year (when the stop year is not missing) whichever occurred earlier. For an enrolled patient without using study medication, default to the same year the patients was enrolled, or the stop year (when the stop year is not missing) whichever occurred earlier;
- If the month is missing:
 - If the start year equals to the stop year, then default to the first dose month or stop month whichever occurred earlier;
 - Otherwise, default to the first dose month or enrollment month for an enrolled patient without using study medication;
- If the day is missing:

Protocol 156-13-211

Laboratory measurements that signal the potential for Hy’s Law will be reported. An incidence table and a listing will be provided for subjects who meet one or combinations of following criteria, without initial findings of cholestasis (ALP activity > 2 × ULN):

- ALT or AST ≥ 3 × ULN
- Bilirubin ≥ 2 × ULN

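### After screening, AST, bilirubin and ALP are drawn mainly on a trigger, so their planned laboratory summaries are selected on abnormality and do not describe the Safety Population

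*Protocol*

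**What the plan says.** **Collection.** Footnote g to Protocol Table 3.7-1 sets one full panel, "A full liver function panel (AST, ALT, alkaline phosphatase, BT) will be done at screening", and then: "All other liver function tests at subsequent visits are for ALT only, unless otherwise clinically indicated". The visit lists agree.

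- Monthly (3.7.1.3): "Collect blood for central laboratory assessments for serum sodium, serum creatinine, and ALT".
- Three-monthly (3.7.1.4): "Collect blood for central laboratory assessments serum sodium, serum creatinine, ALT".
- End of treatment (3.7.1.5): the chemistry panel, with ALT as the only named liver test. Table 3.7.2.2-1 puts AST, bilirubin and ALP in the separate liver function panel, not in the chemistry panel.
- Seven-day follow-up (3.7.1.6): creatinine and ALT.

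Further testing is prompted: "An ALT elevation > 2 × ULN should trigger prompt testing of hepatic function within 72 hours". Protocol 3.7.2.4.1 adds suspicious symptoms or signs as a trigger and asks for at least weekly retesting in the first month while values stay abnormal. The UK version of the protocol has the same ALT-only rule.

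**Reporting.** Protocol 7.5.2.3: "Summary statistics for changes from baseline in clinical laboratory measurements will be provided for the Safety Population". SAP 8 repeats the change-from-baseline plan on all available data. SAP 5.2 restricts summaries to observed values, without imputation. SAP 3.4 maps unscheduled visits into the study windows and keeps the last value in each. SAP Appendix 1 grades AST and total bilirubin. The potential Hy's Law text just before SAP 8.3 says "An incidence table and a listing will be provided for subjects who meet one or combinations of following criteria"; the criteria are ALT or AST ≥3×ULN and bilirubin ≥2×ULN, in the absence of raised ALP.

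The synopsis lists among the safety assessments "serum chemistry tests (including serum transaminases, alkaline phosphatase, bilirubin, and serum sodium".

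**The concern.** Everyone has a screening value for AST, bilirubin and ALP, but only subjects flagged by ALT, symptoms or clinical judgement are likely to have a later one. A by-visit mean change computed on observed values then compares flagged subjects with their own screening result, under a title naming the Safety Population. SAP 3.4 feeds the retests into those visit cells.

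Incidence has the same defect in two forms. With tested subjects as denominator, the proportion is too high whenever the analyte moves with ALT. With all treated subjects as denominator, it is too low, because untested subjects count as free of the event.

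This matters because liver injury is the most notable safety issue named in Protocol 1.3, and Protocol 2.1 says the trial is meant to define the potential for drug-induced liver injury more precisely. An asymptomatic, isolated AST or bilirubin rise in a subject with normal ALT may never be sampled.

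**Working it through.** The plan states no figure on this point. The 2,500 in Protocol 7.1 is an enrolment expectation, and SAP 8 rules out inference. So the check is first a trace of the samples and then an illustration of size.

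**Trace.** None of the visible visit lists after screening schedules AST, bilirubin or ALP. No visible analysis text restricts these analytes to tested subjects, sets a denominator, or separates scheduled from triggered samples.

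**Share tested (q).** Protocol 2.1 gives 4.4% of tolvaptan subjects with ALT >3×ULN over 3 years: 0.044 × 2,500 = 110 tested and 2,390 not. The trigger is lower than 3×ULN, which raises q. Against that, many subjects enter with more than 18 months of exposure, after which Protocol 2.1 describes new elevations as similar to placebo; this lowers q. I therefore assume 3% to 15%, that is 75 to 375 subjects.

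**Mean change.** Let the analyte have correlation r with ALT (an assumption), and let the top share q on ALT be tested. For normal variables the observed mean is shifted by r·φ(c)/q standard deviations, where c = Φ⁻¹(1−q).

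| q | φ(c)/q | r = 0.3 | r = 0.6 | r = 0.9 |
|---|---|---|---|---|
| 3% | 2.27 | 0.68 | 1.36 | 2.04 |
| 4.4% | 2.12 | 0.63 | 1.27 | 1.90 |
| 15% | 1.55 | 0.47 | 0.93 | 1.40 |

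Shifts are in SD, computed before rounding. At r = 0 there is no shift. The model takes the value at the trigger. Because SAP 3.4 keeps the last value in a window, a retest after recovery would reduce the shift.

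**Incidence.** Assume a true rate of 1% and q = 8%, with 4 million simulated bivariate-normal draws. The Safety Population figure is q times the tested figure.

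| r | Tested as denominator | Safety Population as denominator |
|---|---|---|
| 0.3 | 3.3% | 0.08 × 3.31% = 0.26% |
| 0.6 | 7.5% | 0.08 × 7.46% = 0.60% |
| 0.9 | 12.2% | 0.08 × 12.24% = 0.98% |

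The tested denominator overstates the 1% in every row. The Safety Population denominator understates it, though hardly at all when r is near 1.

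**The case against.** The best counter-argument is that part of the relevant text cannot be read. The opening of the SAP laboratory section (8.2) and the end of Protocol 7.5.2.3 are not visible, and some visit items are redacted. A denominator rule or an extra test could sit there. That stands as a limit on the point. It does not remove the explicit ALT-only rule in footnote g or the visible general rules on change from baseline, observed values and visit windows.

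It is also fair that the analysis is descriptive, that a listing will identify individual cases, and that the synopsis names types of test without timing, so triggered tests would fit it. The synopsis point is therefore one of wording.

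A reader might infer four stronger things that the documents do not support.

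- *That isolated AST or bilirubin rises are never counted.* Symptoms, signs or clinical indication can prompt testing. Protocol 3.7.2.4.2 requires a liver eCRF for AST ≥3×ULN or bilirubin ≥2×ULN after normal screening. The SAP table counts subjects meeting a single criterion.
- *That the Hy's frequency is unusable.* A detected ALT >3×ULN has already passed the 2×ULN trigger, so ALT-based cases are largely protected. What remains is AST-only cases, bilirubin rises outside the triggered draws, and the fact that the trigger text does not name the panel.
- *That ALP incidence is planned.* Appendix 1 has no ALP grade; ALP enters only the general change-from-baseline summary and the Hy's exclusion.
- *That the ratio of the two denominators measures the bias.* That ratio is 1/q, about 7-fold at 15% (1/0.15) and 33-fold at 3% (1/0.03). It would be the same if testing were random.

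**Conclusion.** The point holds for AST, bilirubin and ALP after screening. Followed as visibly written, the plan gives by-visit changes, and AST and bilirubin incidences, from subjects selected on abnormal ALT, symptoms or clinical indication. Neither describes the Safety Population. ALT frequencies are unaffected.

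The direction follows from any positive correlation with ALT. The size cannot be fixed from the documents: the shifts of about 0.5 to 2 SD and the incidence figures rest on an assumed tested share of 3–15%, assumed correlations of 0.3 to 0.9, an assumed true rate of 1% and a normal model. No error rate or power is involved. The plan should still be changed, because the stated rules would produce misleading tables on the trial's main safety question. The one reservation is that unseen text in SAP 8.2 or Protocol 7.5.2.3 may already set a denominator.

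**What to change.** In the SAP laboratory section and table shells:

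1. Do not present by-visit mean change from baseline for AST, bilirubin and ALP as Safety Population results.
2. Report post-screening values per triggered episode, or by listing. Include every kind of trigger (ALT, symptom or sign, clinical indication), since limiting reports to ALT-triggered episodes would drop the isolated rises that were found.
3. In the AST and bilirubin incidence tables, show the number tested for each analyte beside the number treated.
4. Label those incidences and the Hy's frequency as detected through triggered testing.

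In the protocol, reconcile the synopsis assessment list with footnote g.

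The cost is SAP wording, table shells and one consistency edit. No new sampling is needed.

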3.7.1 Schedule of Assessments

3.7.1.1 Screening (-30 days to 1 day prior to Baseline)

Screening for eligibility is required for all subjects. The screening and baseline visit may be combined with the last visit from either Trials 156-08-271 or 156-13-210 with all required assessments from each visit performed only once. Therefore, in some cases, if a subject enrolls in this trial from a prior tolvaptan trial, the end of trial or last follow-up visit for that trial and the screening and baseline visit for this one may occur simultaneously. Required assessments for the screening visit are as follows:

1. Obtain subject consent.
2. Obtain subject's new screening identification (ID) assigned by interactive response technology (IRT).
3. Determine subject eligibility through inclusion/exclusion criteria
4. Record demographic information and prior trial identifiers (screening ID, subject ID, site ID, prior tolvaptan ADPKD trial protocol number).
5. Record medical/ADPKD history using prior trial data.
6. Review dietary recommendations and compliance
7. Record vital signs (post-void weight and seated heart rate) and in-clinic calibrated blood pressure (BP) measurement. Record height.
8. Collect blood for serum chemistry, liver function panel (ALT, AST, BT, bilirubin [direct], and alkaline phosphatase), serum sodium, serum creatinine, and hematology and coagulation. Hepatitis testing is optional. If hepatitis testing is performed, then both pre- and post-counseling activities relating to hepatitis testing are to be carried out based on local requirements and best practices.
9. Collect urine for urinalysis, urine osmolality (optional), and urine specific gravity.
10. Perform urine pregnancy test on women of childbearing potential (WOCBP). If positive, a follow-up serum test will be performed.
11. Conduct full physical examination.
12. Enter subject into interactive response technology (IRT) including prior trial identifier/information (protocol number, subject ID), confirmed dose regimen, and scheduled date of next visit.
13. Assess AEs reported as ongoing or resolved from prior trial to determine entry as medical history or ongoing event for this trial.
14. Record ongoing concomitant medications. (This will happen only if the screening visit occurs simultaneously with the last visit from a previous tolvaptan trial).

Protocol 156-13-211

3.7.1.2 Baseline (Day 0)

The baseline visit is the beginning of the treatment period in this trial. At the baseline visit, subjects will retain the subject number assigned in the previous tolvaptan trial, and the following assessments and procedures will be performed:

1. Review inclusion/exclusion criteria.
2. Review dietary recommendations and compliance.
3. CCI [REDACTED]
4. Record vital signs (post-void weight, seated heart rate, and calibrated blood pressure measurement).
5. Dispense at-home urine pregnancy test kits to WOCBP to be used if a menstrual period is missed before the next visit.
6. An optional directed physical examination may be performed to focus on PKD-related signs and symptoms.
7. Assess tolerability/dosing review of investigational medicinal product (IMP).
8. Enroll subject into trial through IRT and obtain IMP.
9. Dispense IMP (sufficient for 1 month or 3 months of dosing based on the subject's required visit schedule for hepatic evaluation as either monthly or every 3 months).
10. Provide subject with dosing instructions to begin on the following day.
11. Record ongoing concomitant medications
12. Assess AEs.

3.7.1.3 Monthly Visit (± 7 days)

The following subjects will return for a monthly visit to assess safety and tolerability of IMP and to monitor liver function.

- Subjects enrolling from the double-blind Trial 156-13-210 will have monthly trial visits/ALT level assessments for the first 18 months while treatment code from Trial 156-13-210 remains blinded, to ensure that they have adequate safety monitoring during this period of susceptibility. Once unblinding occurs, it can be determined which subjects received tolvaptan in Trial 156-13-210. These subjects may have their trial visits/hepatic transaminase monitoring change to every 3 months sooner as their previous tolvaptan exposure in Trial 156-13-210

Protocol 156-13-211

can count towards the 18-month threshold. The investigator will need to discuss the change in frequency with the medical monitor before instituting the change.

- Subjects from prior tolvaptan trials other than Trial 156-08-271 will have monthly trial visits/ALT level assessments for the first 18 months. After that, the trial visits/ALT monitoring will be conducted every 3 months after the change in frequency is confirmed with the medical monitor.
- Subjects enrolling from the open-label Trial 156-08-271 who have greater than 18 months of exposure to tolvaptan will have trial visits/ALT monitoring conducted every 3 months.

The following will be assessments will be completed:

1. Review dietary recommendations and compliance.
2. CCI [REDACTED]
3. Record vital signs (post-void weight, seated heart rate, and calibrated blood pressure measurement).
4. Collect blood for central laboratory assessments for serum sodium, serum creatinine, and ALT (see [Section 3.7.2.4](#)).
5. CCI [REDACTED]
6. CCI [REDACTED]
7. Urinalysis, urine osmolality (optional), urine specific gravity.
8. Perform urine pregnancy test on WOCBP (every 3 months). If positive, a follow-up serum test will be performed.
9. Dispense at-home urine pregnancy test kits to WOCBP, as required.
10. An optional directed physical examination may be performed to focus on PKD-related signs and symptoms.
11. Assess tolerability/dosing review of IMP.
12. Enter subject status in IRT, including any dose regimen changes and obtain IMP assignment.
13. Collect and reconcile returned IMP, assess compliance.
14. Dispense IMP based on subject's required visit schedule, and provide subject with dosing instructions.
15. Update concomitant medications.
16. Assess AEs.

Protocol 156-13-211

3.7.1.4 Every 3 Months (\pm 14 days)

1. Review dietary recommendations and compliance.
2. CCI [REDACTED]
3. Record vital signs (post-void weight, seated heart rate, and calibrated blood pressure measurement).
4. Collect blood for central laboratory assessments serum sodium, serum creatinine, ALT (see [Section 3.7.2.4](#)).
5. CCI [REDACTED]
6. Urinalysis, urine osmolality (optional), urine specific gravity.
7. Perform urine pregnancy test on WOCBP. If positive, a follow-up serum test will be performed.
8. Dispense at-home urine pregnancy test kits to WOCBP, as required.
9. CCI [REDACTED]
10. An optional directed physical examination may be performed to focus on PKD-related signs and symptoms.
11. Assess tolerability/dosing review of IMP.
12. Enter subject status in IRT, including any dose-regimen changes and obtain IMP assignment.
13. Collect and reconcile returned IMP; assess compliance.
14. Enter subject status in IRT, including any dose-regimen changes.
15. Dispense IMP based on subject's visit schedule, and provide subject with dosing instructions.
16. Update concomitant medications.
17. Assess AEs.

